If both eyes from the same patient meet eligibility criteria, each eye will be included in the study database with a unique identifier and eyes will be paired in the electronic data capture system (EDC). Study procedures, and evaluations are described in detail in Sections 9 and 10 and data to be collected are summarized in Table 2: surgery data (procedure performed, XEN 45 Gel Stent and cataract related complication, anti-metabolite and/or antifibrotic therapy used), IOP level, number of topical IOP-lowering medications taken, eye examination (visual field exam, best corrected visual acuity...), interventions performed on the study eyes, IOP lowering medications, and AESIs. Safety events to be collected are described in Section 10.9.

Data extraction may begin as soon as sites are initiated. This study will collect anonymized data (i.e. no list of identifier will be kept by the sites and once data are entered in the system, investigators, study personnel and sponsor will not be able to identify patients), therefore no informed consent will be requested from patients.

Table 2 displays the time frame during which study variables will be collected.

Table 2 Schedule of Data Collection

Data Collected	Baseline^[a]	XEN 45 Gel Stent Implantation	Study Period^[b]
Eligibility Assessment	X		
Demography	X		
Ocular and Glaucoma Medical History	X		
Surgery-related data		X	
Number of IOP-lowering medications	X		X
Visual field exam^[c]	X		X
Intraocular pressure	X		X
Best corrected visual acuity	X		X
Needling procedures			X
Secondary surgical intervention for glaucoma			X
Adverse events of special interest			X

IOP=intra-ocular pressure.

[a] Baseline is defined as the day when the decision was made to implant XEN 45 Gel Stent.

[b] The study period is defined as the period between XEN 45 Gel Stent implantation and 1 October 2018. For each eye selected, all retrospective data available from baseline until 1 October 2018 or until the date on which the patient received a SSI for glaucoma, whichever occurs first, will be extracted from existing medical records.

[c] If no visual field exam is available at baseline, a value measured up to 12 months prior to baseline is acceptable. In the event that more than one value is available in this 12-month period, the value closest to the baseline date will be used.

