10.3 Ocular and Glaucoma Medical History

Ocular history of the selected eye will be collected, such as glaucoma diagnosis, previous ocular and glaucoma procedures, previous ocular medications (including whether or not eye is treated with Diamox on the day when decision was taken to implant XEN 45 Gel Stent) and ocular pathologies observed at baseline. Glaucoma stage at baseline will be determined by investigators based on visual field assessment.

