14.2.5 Secondary Objectives

14.2.5.1 Change in IOP and Number of Topical IOP-Lowering Medications 4 Years after XEN 45 Gel Stent Implantation

Change in IOP from medicated baseline and change in the number of topical IOP-lowering medications compared to baseline will be summarized descriptively at Year 4 after XEN 45 Gel Stent implantation in eyes from the Analysis Population with at least 4 years of follow-up data and were not treated with Diamox on the day when decision was taken to implant XEN 45 Gel Stent.

14.2.5.2 Success over the Long Term of following implantation of the XEN 45 Gel Stent

Number and proportion of eyes achieving a 20% reduction in IOP from medicated baseline, and number and proportion of eyes with an IOP <18 mmHg, IOP <17 mmHg, ..., down to IOP <12 mmHg will be described at all time-points of interest in eyes from the Analysis Population that did not undergo SSI for glaucoma, did not have clinical hypotony, and were not treated with Diamox on the day when decision was taken to implant XEN 45 Gel Stent.

The number and proportion of eyes achieving qualified or complete success at 3 and 4 years after XEN 45 Gel Stent implantation will be summarized descriptively. Analyses will be conducted in the Analysis Population. Kaplan-Meier analyses will be conducted to analyze time from initial procedure to SSI for glaucoma.

14.2.5.3 Safety over the long term following implantation of the XEN 45 Gel Stent

Surgical complications and post-operative AESIs will be summarized descriptively using frequencies and percentages. Analyses will be performed in the Analysis Population.

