1.4. Key Variable Definitions

Qualified success of implantation of the XEN 45 Gel Stent will be defined as $\geq 20\%$ reduction from medicated baseline with no Secondary Surgical Intervention (SSI) for glaucoma and no clinical hypotony while staying on the same number or fewer topical IOP-lowering medications than at baseline.

Complete success of implantation of the XEN 45 Gel Stent will be defined as $\geq 20\%$ reduction from medicated baseline with no SSI for glaucoma and no clinical hypotony while taking no topical IOP-lowering medications.

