4.3. Disease progression

Ocular medical history will be summarised descriptively in the Safety Population overall and not by the time windows specified. Needling procedures will be summarized in the Safety Population by the time windows indicated in Section 4.1. Anti-metabolite/anti-fibrotic use will be described during the stent implantation, during conjunctiva bleb revision (if applicable), during needling procedures (if applicable), and also when used alone. Anti-metabolite/anti-fibrotic use during needling procedures will be determined based on the date of each anti-metabolite/anti-fibrotic use and date of the needling procedure; the same date assumes that the anti-metabolite/anti-fibrotic was used in conjunction with the needling procedure. IOP lowering medications (oral) will be described at baseline and post-implantation in the Effectiveness Population by class of medication (carbonic anhydrase inhibitors or alpha-agonist hypotensive agent). Visual field exam will be summarised descriptively at baseline and for all time points of interest (as described in Section 4.1) in the Safety Population. All BCVA values will be converted to logarithm of the minimum angle of resolution (logMAR) units.³ To do this, Snellen values will be converted by taking the negative base 10 logarithm of the decimal. ETDRS letters will be converted to approximate Snellen scores by the following formula.

$$\text{Snellen} \cong \exp \left\{ \frac{1}{50} (\text{ETDRS} - 85) \right\}.$$

This will then be converted into logMAR units using the negative base 10 logarithm of the decimal as above. Any non-numerical BCVA values (i.e. including count fingers, hand movement, light perception and non-light perception) will also be converted to logMAR units as described below:⁴

Non-numerical BCVA value	LogMAR
Count fingers (CF)	1.8
Hand movement (HM)	2.3

Light perception (LP)	2.8
No light perception (NLP)	3.0

4.4. Change in IOP and number of topical IOP-lowering medications after XEN 45 gel stent implantation

Change in IOP from medicated baseline and change in the number of topical IOP-lowering medications will be summarised. Change in number of IOP-lowering medications will be made by examining the class of the medication as follows:

- Beta Blocking Agents
- Carbonic Anhydrase Inhibitors
- Parasympathomimetics
- Prostaglandin Analogues
- Sympathomimetics In Glaucoma Therapy

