These will be compared to baseline and will be summarised descriptively at months 12, 24, 36 and 48 after XEN 45 Gel Stent implantation in eyes from the Effectiveness Population. Analyses will only include those with available data at each of the time points of interest and those who were not treated with Diamox on the day when decision was taken to implant XEN 45 Gel Stent.

A paired t-test will be applied for statistical analysis in comparing the difference between post baseline to baseline values. The assumptions of the test are as follows:

- No significant outliers in the differences between time points (which can be tested by a scatter plot of the data)
- The distribution of the differences in the dependent variable between the two time points should approximately follow a normal distribution (which can be tested through the Shapiro-Wilk test)
- The dependent variable is measured on a continuous scale

If the assumptions of the t-test are heavily violated then the non-parametric analogue (Wilcoxon Signed-Rank test) should be used to test the difference between time points.

4.4.1. Success over the long term of following implantation of the XEN 45 Gel Stent

Number and proportion of eyes achieving a 20% reduction in IOP from medicated baseline, and number and proportion of eyes with an IOP between 6 and 18 mmHg, IOP between 6 and 17 mmHg, ..., down to IOP between 6 and 12 mmHg will be described by the time-windows described in Section 4.1 in eyes from the Effectiveness Population that did not undergo SSI for glaucoma, and were not treated with Diamox on the day when decision was taken to implant XEN 45 Gel Stent.

The number and proportion of eyes achieving qualified or complete success at each time point of interest (i.e. 12, 24, 36, 48 and >51 months) after XEN 45 Gel Stent implantation will be summarised descriptively. Analyses will be conducted in the Effectiveness Population.

The time from XEN 45 Gel Stent implantation to SSI for glaucoma will be described using Kaplan Meier curves.

4.5. Safety over the long term following implantation of the XEN 45 Gel Stent

Surgical complications and post-operative AESIs will be summarised descriptively using frequencies and percentages.

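### Oral IOP-lowering treatment at follow-up is tabulated but never enters the success analysis, and decision-day Diamox eyes are dropped from the neighbouring analyses but not from success

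*SAP*

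**What the plan says.** **Success.** SAP 1.4 and protocol 6.2 give the same two definitions. Both categories require at least a 20% fall from medicated baseline IOP and freedom from glaucoma reintervention and clinical hypotony. Qualified success allows no more topical agents than at baseline. Complete success is the same "with no SSI for glaucoma and no clinical hypotony while taking no topical IOP-lowering medications". Neither definition mentions oral treatment.

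**Oral drugs after implantation.** SAP 4.3 does cover them, as a description: "IOP lowering medications (oral) will be described at baseline and post-implantation in the Effectiveness Population by class of medication".

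**Diamox.** Protocol 10.3 collects it with the ocular history, "including whether or not eye is treated with Diamox on the day when decision was taken to implant XEN 45 Gel Stent". SAP 4.4 limits the IOP and medication change analyses to eyes with data and to "those who were not treated with Diamox on the day when decision was taken to implant XEN 45 Gel Stent". SAP 4.4.1 applies the same limit to the 20% and IOP-threshold proportions. Protocol 14.2.4, 14.2.5.1 and 14.2.5.2 follow the same pattern. The success sentences carry no such limit. SAP 4.4.1 summarises "The number and proportion of eyes achieving qualified or complete success at each time point of interest" in the Effectiveness Population, and protocol 14.2.5.2 summarises "The number and proportion of eyes achieving qualified or complete success at 3 and 4 years after XEN 45 Gel Stent implantation" in the Analysis Population. Neither population definition (SAP 4, protocol 14.2.1) mentions Diamox.

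**Medication count.** The SAP 4.4 heading and opening sentence say topical. The next sentence, "Change in number of IOP-lowering medications will be made by examining the class of the medication as follows", omits the word and introduces a list that includes carbonic anhydrase inhibitors, a class that SAP 4.3 also names for oral drugs.

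**The concern.** Complete success will be read as pressure control without medication. As written, it means control without drops. If some eyes reach it on an oral agent, the result tables will not show which ones or how many.

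The plan's own handling of Diamox makes this harder to pass over. By leaving decision-day Diamox eyes out of the change and threshold analyses, it treats that therapy as relevant to interpreting IOP. It then applies no such thinking at follow-up, and it does not apply the baseline rule to success. At stake is the interpretation of one secondary outcome, and whether the success rows can be compared with the 20% rows beside them.

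**Working it through.** **1. The plan's own figure.** Protocol 14.1 takes a mean change of −5.6 mmHg, SD 6.32, and 60 eyes. The half-length is 1.96 × 6.32 / √60 = 1.60 mmHg, so the interval is −7.2 to −4.0, as stated. This concerns mean IOP change and says nothing about oral treatment. It is used here only as the source of N = 60. N = 150 is the planned number of selected eyes.

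**2. Following one eye through the plan.** Take an eye at Month 36 with IOP at least 20% below baseline, no drops, an oral agent, no reintervention and no clinical hypotony.
- SAP 1.4: complete success.
- SAP 4.3: counted among post-implantation oral users.
- SAP 4.4.1: no step joins these two facts.

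The SAP 4.3 table names no visit window. Under SAP 4.1 the 33-to-39-month window serves IOP and the medication number only, and other data fall by default into yearly bands. A Month 38 visit would therefore sit in the Month 36 window for IOP and in the band from 36 to 48 months for other data.

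**3. Size of the oral-use gap.** If k eyes meet all other criteria and have a recorded oral agent, the rate falls by k/N. The values of k are illustrations.

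| k | N = 60 | N = 150 |
|---|---|---|
| 1 | 1.7 points | 0.7 points |
| 3 | 5.0 points | 2.0 points |
| 6 | 10.0 points | 4.0 points |

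Another way to set the range is to assume that complete success is 20% to 40% and that 2% to 10% of those successes are on an oral agent. The fall is then 0.20 × 0.02 = 0.4 points to 0.40 × 0.10 = 4.0 points.

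Month 48 may have fewer than 60 eyes. Its window opens at Month 45, and 1 October 2018 minus 45 months is 1 January 2015. Eyes implanted after that date, which protocol 9.2 allows if accrual is short, cannot contribute.

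**4. Which eyes each analysis leaves out.**

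| Analysis | Decision-day Diamox | SSI | Clinical hypotony |
|---|---|---|---|
| 20% and threshold proportions | left out | left out | left out in protocol 14.2.5.2 only |
| Qualified and complete success | kept | kept, as failures | kept, as failures |

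The two rows differ in more than Diamox, so aligning Diamox alone does not make the denominators equal.

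**5. Size of the Diamox difference.** With S successes among N eyes, of which m are Diamox eyes with s successes, the rate without them is (S − s)/(N − m). Assume S = 30 and N = 60, so the rate with them is 50.0%.

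| m | none succeed | same 50% rate | all succeed |
|---|---|---|---|
| 3 | 30/57 = 52.6% | 28.5/57 = 50.0% | 27/57 = 47.4% |
| 6 | 30/54 = 55.6% | 27/54 = 50.0% | 24/54 = 44.4% |

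**The case against.** The topical-only definition is deliberate. It runs through the objectives, the outcomes and the success definitions of both documents, and the protocol and SAP agree on it. Oral drugs have their own table in SAP 4.3. Asking for success under a stricter definition can look like reviewer preference, with no rate of oral use behind it.

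The data are also thin. Protocol 7.1 lists "interventions performed on the study eyes, IOP lowering medications, and AESIs" separately from the topical number, and protocol 12 codes IOP-lowering drugs. But the minimum dataset (protocol 8.2.3, SAP 1.7) and the IOP item in SAP 1.8 require only the topical number, and protocol 14.3.3 rules out queries. An oral drug acts on both eyes and may have been given for the other one.

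Much of this stands. The definition should not change, and a reader who infers that the plan ignores oral drugs after implantation would be wrong. The data limits also mean that no recorded oral use would not prove no use, and that a flagged rate is not a strict bound in either direction. What does not stand is that SAP 4.3 settles the matter: its table cannot say whether any complete success was on oral treatment at the visit that counted.

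A reader might also infer that the SAP 4.4 medication count includes oral agents. The heading and opening sentence of that section both say topical, so the missing word is an editorial slip.

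**Conclusion.** The point holds and is minor. Recorded oral use at the Month 36 or 48 visit has no consequence for success, and the Diamox rule covers the 20% proportion but not the success categories built on the same 20% reduction. The effect is 1.7 points per reclassified eye of 60, and more if fewer eyes are available. How many eyes are affected is unknown and may be none.

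Two stronger readings are not supported. One is that the success rates are inflated: the documents give no rate of oral use, so only the possibility is shown. The other is that keeping Diamox eyes shifts success in a known direction: the tables above show that it can go up, down or nowhere.

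The argument from Diamox assumes that it is a systemic agent, since the documents do not state its route. The finding about oral use at follow-up does not depend on that assumption.

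**What to change.** Keep the protocol definitions as the main analysis. In SAP 4.4.1, at Months 36 and 48, add:

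- **(a) Oral-use sensitivity rows.** Count eyes with a recorded oral IOP-lowering agent at the window visit as not complete successes. Count eyes that newly started one since baseline as not qualified successes. Show the number of flagged eyes.
- **(b) A Diamox row.** Report qualified and complete success without decision-day Diamox eyes, keeping SSI and clinical-hypotony eyes as failures. Describe it as aligning the Diamox handling only, not the whole denominator.
- **A footnote.** Oral use is recorded for a patient, may have been for the other eye and may be under-recorded, so neither zero recorded use nor the flagged rate is a strict bound.

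As a separate editorial correction, insert the word topical in the SAP 4.4 class sentence.

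The cost is a few table rows, one flag and one footnote, with no change to any protocol endpoint. SAP 4 stratifies by three procedure groups and by primary eye or all eyes, so each row is repeated 3 × 2 = 6 times. Incomplete oral records will misclassify some eyes, including well-controlled study eyes whose patient took the drug for the other eye. The success rates in (a) can only equal or fall below the main ones.

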1.5. Outcome Variables

Performance outcomes:

- Change in IOP from medicated baseline to 3 years after XEN 45 Gel Stent implantation
- Change in IOP from medicated baseline to 4 years after XEN 45 Gel Stent implantation
- Study pre-defined IOP outcomes achieved while staying on the same number or fewer topical IOP-lowering medications and without clinical hypotony: 20% reduction from medicated baseline, as well as IOP below 12 mmHg and through to IOP below 18 mmHg
- Change in the number of topical IOP-lowering medications from medicated baseline to 3 years after XEN 45 Gel Stent implantation
- Change in the number of topical IOP-lowering medications from medicated baseline to 4 years after XEN 45 Gel Stent implantation
- Qualified or complete success 3 years after XEN 45 Gel Stent implantation
- Qualified or complete success 4 years after XEN 45 Gel Stent implantation

Safety outcomes:

- Adverse events of special interest (AESIs), as defined in Section 1.8 below.

1.6. Study Design

This is a retrospective, non-interventional, observational, multi-centre, chart review study conducted in patients who underwent placement of the XEN 45 Gel Stent as a standalone procedure or in combination with phacoemulsification from 1 January 2014 to 1 October 2015.

For each eligible eye, all retrospective data available from baseline (i.e. day when decision was made to implant XEN 45 Gel Stent) until Last Visit (i.e. date of the last follow-up visit available prior to 1 October 2018 or date on which the patient had a SSI for glaucoma, whichever occurs first) are extracted from existing medical records into the electronic CRF (eCRF) in Dacima.

If both eyes from the same patient meet eligibility criteria, each eye is included in the study database with a unique identifier and eyes are paired in the electronic data capture system (EDC). See section 4 for how bilateral eyes included in the study are handled in the analyses.

1.7. Study Population

The study population includes patients with one or both eyes with open angle glaucoma that underwent XEN 45 Gel Stent implantation.

Patients meeting the following criteria are eligible for participation in the study:

1. Eye treated with XEN 45 Gel Stent for open angle glaucoma as a standalone procedure or in combination with phacoemulsification
2. XEN 45 Gel Stent was implanted between 1 January 2014 and 1 October 2015
3. Charts contain minimum required data (age, gender, IOP at baseline until last visit, number of topical IOP-lowering medications prescribed for the study eye from baseline until last visit, date of the SSI for glaucoma if applicable)

1.8. Data Collection

Data are being collected from patients' medical records using an eCRF on the Dacima platform. The eCRF includes edit and range checks to minimize the amount of missing or invalid data.

[figure not shown]
The schedule for data collection is presented below:

Data Collected	Baseline[a]	XEN 45 Gel Stent Implantation	Study Period[b]
Eligibility Assessment	X		
Demography	X		
Ocular and Glaucoma Medical History	X		
Surgery-related data		X	
Number of IOP-lowering medications	X		X
Visual field exam	X		X
Intraocular pressure	X		X
Best corrected visual acuity	X		X
Needling procedures			X
Secondary surgical intervention for glaucoma			X
Adverse events of special interest			X

IOP=intra-ocular pressure.

[figure not shown]
[a] Baseline is defined as the day when the decision was made to implant XEN 45 Gel Stent.

[b] The study period is defined as the period between XEN 45 Gel Stent implantation and 1 October 2018. For each eye selected, all retrospective data available from baseline until 1 October 2018 or until the date on which the patient received a SSI for glaucoma, whichever occurs first, are from existing medical records.

Data collected includes:

- Demographics
- Selected eye characteristics (oculus dexter vs. oculus sinister), along with information about whether patient's other eye was also selected.
- Ocular and Glaucoma Medical History
- Surgery-Related Data
 - Use of anti-metabolite and/or anti-fibrotic
 - Procedure performed (i.e., XEN 45 Gel Stent implantation alone or phacoemulsification + XEN 45 Gel Stent implantation)
 - XEN 45 Gel Stent and cataract-related complications
- Intraocular Pressure Data
 - IOP-related data, i.e. IOP and number of topical IOP-lowering medications
- Visual Field Exam
- Best Corrected Visual Acuity (BCVA), including method used
- Needling Procedures
- Secondary Surgical Intervention (nature and date, if applicable)
- Adverse events of special interest (AESI):
 - Anterior chamber defects:
 - Shallow with peripheral iridocorneal touch
 - Flat with irido-corneal touch extending to the pupil
 - Bleb leak
 - Blebitis
 - Choroidal effusion, hemorrhage or mixed effusion hemorrhage recorded as follows:
 - Extending posterior to the equator
 - Obscuring disc or macula
 - With choroids touching in the centre of the eye
 - Persistent choroidal effusion, hemorrhage or mixed effusion hemorrhage occurring > 30 days post-operation
 - Corneal oedema:
 - Transient corneal decompensation / edema (<30 days)
 - Persistent corneal decompensation / edema (>30 days)
 - Mild corneal decompensation / edema

[figure not shown]

-
- Moderate corneal decompensation / edema
 - Severe corneal decompensation / edema
 - Cyclodialysis
 - Endophthalmitis
 - Hyphema
 - ≥ 2 mm in height (layered) at any time; present or arising > 30 days postoperatively
 - Persistent hypotony: IOP < 6 mmHg, present at two consecutive visits postoperatively > 30 days apart
 - Clinical hypotony: vision reduction (2 lines or more) related to macular changes consistent with hypotony maculopathy (macular folds), optic disc edema, and/or serious choroidal detachments because of low IOP
 - Implant blockage in the anterior chamber
 - Implant exposure or extrusion
 - Implant fracture
 - Implant migration
 - Implant repositioning requiring surgical intervention
 - Implant touching iris
 - Implant touching cornea
 - Iridodialysis
 - Iritis (requiring treatment after the postoperative medication taper)
 - Macular edema
 - Ptosis
 - Retinal detachment
 - Suture abscess or other local infection
 - Vitreous hemorrhage
 - Any other adverse event that leads to permanent visual impairment or requires surgical or medical intervention to prevent permanent visual impairment

2. Sample Size

A sample size of 150 patient eyes was selected, as it is anticipated that this will allow for the inclusion of a minimum of 60 independent study eyes have at least 3 years of follow-up data without a SSI for glaucoma after the initial implant with XEN 45 Gel Stent. Based on the Allergan study MS-001, for month 36 the 95% confidence interval (CI) of the projected mean IOP reduction afforded by a sample of 60 study eyes is -7.2 to -4.0 mmHg. That is, the half-length of the interval is 1.6 mmHg, which provides a reasonable precision for the estimate of the projected mean reduction in IOP.

3. Data Handling

